2 METHODS

Pregnant women in labor at study health facilities who appear to be ≥28 weeks gestational age by best clinical estimate with a live fetus pregnancy will be screened for eligibility (see **Section 2.2**) by research staff starting at the time of admission and continuously during the hospitalization. Gestational age will be determined using the “best estimate” algorithm that is currently used in the GN MNH registry. Those eligible will be consented. Those consented will be randomized to receive a single dose of azithromycin 2 g or identical placebo to be given and directly observed during labor. Because of the ease of storage of azithromycin, sequentially prepared medications in identical packages following the randomization sequence will be available and dispensed by the study staff. The rest of the care will be provided according to the local standard of care. Women will be followed up until discharge and surveillance maintained (in-person), with visits at 3 days, 7 days, and 42 days after delivery as has generally been done in the Global Network to ascertain study outcomes.

We will apply the recently recommended “simple and actionable” WHO definition of sepsis in a 2017 statement endorsed by multiple international organizations. The definition of sepsis includes a suspicion of infection and the presence of organ dysfunction based on clinical findings.¹⁵

To further ensure more objective ascertainment of the sepsis outcome, we propose that the DCC will prospectively define a process for defining criteria for a masked centralized review and adjudication of all

cases of infection to ensure conformity with the proposed definition. This approach of adjudication is applied to validate infection in many trials including our recently completed ASPIRIN trial.³⁸ This approach to adjudication has some similarities to the near-miss classification for adjudication in women delivering in the Global Network sites that was done recently.³⁹

2.1 Study Design

This study is a masked, placebo-controlled RCT. The investigational regimen is 2 g of azithromycin and the comparison arm is an identical placebo which is given orally. Both groups will also receive the standard of care during labor, delivery and postpartum per local standards.

2.2 Study Population/Location

Pregnant women laboring in health facilities of the eight Global Network sites/other health facilities will be eligible. The Global Network sites are described in **Appendix 1**. Health facilities may include any hospitals and health centers where women routinely deliver within the study sites.

2.2.1 Inclusion Criteria

- Pregnant women in labor ≥ 28 weeks GA (by best estimate) with a pregnancy with one or more live fetuses who plan to deliver vaginally in a facility.
- Admitted to health facility with clear plan for spontaneous or induced delivery.
- Live fetus must be confirmed via presence of a fetal heart rate prior to randomization.
- ≥ 18 years of age or minors 14-17 years of age in countries where married or pregnant minors (or their authorized representatives) are legally permitted to give consent.
- Have provided written informed consent [Note: written informed consent may be obtained during antenatal care, but verbal re-confirmation may be needed (per local regulations) at the time of randomization].

2.2.2 Exclusion Criteria

- Non-emancipated minors (as per local regulations)
- Evidence of chorioamnionitis or other infection requiring antibiotic therapy at time of eligibility (however, women given single prophylactic antibiotics with no plans to continue after delivery should not be excluded).
- Arrhythmia or known history of cardiomyopathy.
- Allergy to azithromycin or other macrolides that is self-reported or documented in the medical record.
- Any use of azithromycin, erythromycin, or other macrolide in the 3 days or less prior to randomization.
- Plan for cesarean delivery prior to randomization.
- Preterm labor undergoing management with no immediate plan to proceed to delivery.
- Advanced stage of labor (>6 cm or 10 cm cervical dilation per local standards) and pushing **or** too distressed to understand, confirm, or give informed consent **regardless** of cervical dilation.
- Are not capable of giving consent due to other health problems such as obstetric emergencies (for example, antepartum haemorrhage) or mental disorder.
- Any other medical conditions that may be considered a contraindication per the judgment of the site investigator.
- Previous randomization in the trial.

Sites may choose to obtain written consent during antenatal care from pregnant women of the age of consent who plan to deliver vaginally in a facility and have no known medical exclusions. In this case, study staff must fully assess and confirm eligibility at the time of randomization. It may also be necessary to verbally re-confirm consent at the time of randomization, if required by local regulations. If it is determined that the study needs to be extended to accrue the planned sample size for HR cohort, then women who deliver prior to meeting HR criteria for randomization will be excluded.

2.3 Study Intervention and Comparison

The study intervention is a single 2 g dose of directly observed oral azithromycin, to be administered as four 500 mg pills or tablets directly after randomization. By random allocation, participants will receive 2 g of oral azithromycin vs. placebo. We will design the placebo with the assistance of a reputable pharmacy/pharmaceutical company, using identical capsules or pills containing azithromycin 2 g or a matching placebo (non-antimicrobial agent) to accomplish masking. All of the participants' obstetric care will be similar for all both arms and consist of the routinely available care at each center.

2.4 Detailed Study Procedures

2.4.1 Community Sensitization

Local health providers will receive sensitization about the study to foster communication and collaboration at the facilities where enrollment will take place. In addition, pregnant women and their families in the enrollment area will receive information about the study during antenatal care (ANC) visits to facilitate recruitment and comprehension during the consenting process. Sites may choose to consent women during these sensitization sessions, prior to labor; however, confirmation of eligibility and consent will be required during the screening process described in **Section 2.4.2 and 2.4.3**.

2.4.2 Screening

Women in labor in defined health facilities (both hospitals and health centers) will be identified by research staff. A brief review of eligibility will be made to determine whether the patient is in labor and does not meet any of the exclusion criteria. If a contraindication to participation in the trial is found, the woman will be excluded from the trial at this point.

2.4.3 Consent

Before a woman participates in the trial, the research staff must obtain her informed consent to voluntarily take part in the study. Consent will be obtained from women ≥ 18 years of age or minors 14-17 years of age in countries where married or pregnant minors (or their authorized representatives) are legally permitted to give consent. When enrolling minors, we will follow the in-country policies for human research protection and the guidelines approved by the local ethical review committees (ERCs). In the case of pregnant minors, this may require that written consent is obtained from her parents/guardians or husband, with written assent from the minor.

Potential participants will be screened and enrolled in the study upon admission for delivery; therefore, consent will be obtained during labor. Consent should be obtained as early as possible during the intrapartum period and must be obtained prior to the cervical dilation limit approved by local authorities (e.g. either > 6 cm or 10 cm) and/or pushing, as assessed from clinical exam by health facility staff. It is not feasible to wait because the intervention must be given before delivery. Research sites

may choose to obtain initial consent during ANC; however, in this situation, confirmation of consent will be required during the screening and enrollment process.

If consent is obtained during labor, study staff will make necessary accommodations to ensure that the laboring women can comprehend the information presented during the consent process. Potential participants who present in labor can take as much time as needed to consider participation while in labor and will be able to discuss the study with family/friends if desired before deciding on participation. If the participant cannot read, the form will be read aloud to her by a person unaffiliated with the study. Alternatively, the Research Coordinator or a designate may read the consent, but in the presence of a witness who is unaffiliated with the research study. Potential participants will be given an opportunity to discuss the study procedures and ask questions. Additional details are provided in the study Manual of Procedures.

Fair balance will be maintained while describing the risks and benefits of participation in the study. No undue pressure will be placed on the potential participant to enroll in the trial. It will further be explained that lack of participation will not affect the usual and anticipated standard of care. As the literacy levels will vary and may be a challenge, the consent process will include a verbal review of the consent form.

After the potential participant has read the consent form, but before she signs, the research staff will show her a sample study pill and confirm that she is willing and able to take the study pill as prescribed. Only if she is willing to commit to taking the pill will she be enrolled; otherwise, this will be recorded as a refusal of consent. Following review of the consent, the potential participant (or parent/guardian) will be asked to sign the form. If the potential participant (or parent/guardian) is unable to sign her name, she will be asked to use her thumbprint to indicate written approval. In both cases, the unaffiliated person will also sign the consent form. Both the research staff and the study participant retain signed copies of the form.

An eligible woman may refuse to participate in the trial at the time of recruitment. This will be recorded in the Screening and Recruitment Form. She may also choose to withdraw from the study at any time after enrollment. This will be recorded on the Withdrawal/Termination Form.

All research staff responsible for obtaining consent will be trained and certified in the protection of human subjects and the study-specific consent procedures. A model written informed consent form, developed according to the requirements of the U.S. Office of Research Protections (OHRP), is found in **appendix 2**. Each site may modify the model consent to conform to local standards, but the OHRP required elements must be maintained. The research sites will also be responsible for translating the consent form into the appropriate language(s) for their local context.

Global Network countries with legislation regarding the need to videotape consents will comply with the country regulations; however, this is not part of the consent form requirements. This will not be required by protocol but rather decided by each site so as to comply with local rules and regulations.

2.4.4 Masking

Both the azithromycin and placebo will be procured from the same manufacturer. The packaging will be standardized across sites and will be labeled as: "Azithromycin 2 g or Placebo", with the expiration date and a unique identifier. A certificate of authenticity will likewise be provided.

Clinical and research staff as well as the women will be masked to treatment status unless there is a serious adverse event potentially related to the treatment modality that requires unmasking for safety reasons. There will be one pharmacist at each site who will monitor randomization, drug supply, and safety. Under the instruction of the DCC, the study pharmacist will be trained and authorized to apply un-masking procedures, if concerns about randomization or participant safety are identified.

2.4.5 Randomization Procedures

Randomization of participants will be carried out to obtain a 1:1 allocation ratio between the treatment and placebo arms. Randomization will be stratified by site. A computer algorithm generated by the data coordinating center (DCC) will create the random assignment to one of the treatment arms based on randomly permuted block design with randomly varied block sizes. The block sizes will be known only by the DCC personnel. Each site will receive a lot of the study drug to be distributed sequentially at the participating health facilities which are randomizing women for the study site.

2.4.6 Monitoring before Discharge

Routine post-delivery care will be provided to participants by their clinical providers who will be masked to the study interventions. Research staff (also masked to study medications) trained in obstetric and perinatal outcomes abstraction will be responsible for collecting research data from participant medical records or directly from participants, as relevant, before discharge. Data needed to determine sepsis will include temperature (fever or hypothermia) essentially, plus one or more of heart rate (tachycardia), blood pressure (hypotension), respiratory rate (tachypnea or distress), clinical exam (jaundice or altered mental status) and urine output (low) and a suspicion of infection by the clinical provider or research team. Maternal and neonatal outcomes will be evaluated in the hospital following the delivery (on an ongoing basis until discharge). All participants will be asked to agree to maternal/infant medical record release to abstract information for outcome assessment as part of the consent form. In addition, participants will be educated about the signs and symptoms of infection and other study outcomes and encouraged to call the research team with any concerns.

2.4.7 Monitoring after Discharge

After discharge, study staff will contact participants at the following timepoints:

- In-person visits will be conducted at 3-day, 7-day, and 42-day postpartum to identify maternal or infant infection, unexpected medical visits, side effects, and other study outcomes. WHO criteria for infections will be used and included in the data collection forms. In the case of suspected infection, research staff will collect specimens (e.g. blood, urine, or pus from wound or drained abscesses), as is feasible, in order to identify individual infectious agents.
- Supplemental phone contacts will be conducted at 14-day and 28-day postpartum to review maternal and neonatal signs of infection using WHO criteria. If signs of infection are identified during the review, participants will be asked to visit a study facility for further assessment. These supplemental contacts will reinforce the participants' ability to self-assess for signs of maternal and neonatal infection and improve identification of infection between the 7-day and 42-day postpartum visits. If phone contact is not feasible, in-person visits may be conducted.

[figure not shown]
If indicated, records of unscheduled visits to any health facility prior to the routine study visits will be obtained and reviewed to ascertain study outcomes. Treating providers may also be called if clarification is needed. Based on the scheduled visits, study staff will identify any unscheduled visits or readmissions

that occurred in the interim. Readmissions and related diagnoses identified during follow-up visits will be then be validated through medical record review.

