2.7 Other Neonatal Outcomes

- a. Other neonatal infections (e.g., eye infection, skin infection, omphalitis, urinary tract infection, respiratory rate ≥ 60 breaths/minute).
- b. Neonatal initial hospital length of stay, defined as time of delivery until initial discharge (time may vary by site).
- c. Neonatal readmission within 42 days of delivery.
- d. Neonatal admission to special care units.
- e. Neonatal unscheduled visit for care.
- f. Neonatal death due to sepsis using the Global Network algorithm for causes of death.
- g. Pyloric stenosis within 42 days of delivery, defined as clinical suspicion based on severe vomiting leading to death, surgical intervention (pyloromyotomy) as verified from medical records, or radiological confirmation.

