2.8 Safety Monitoring

Surveillance of maternal side effects including nausea, vomiting, and diarrhea/loose stools, abdominal pain, vaginitis, and dizziness potentially associated with azithromycin will be conducted during labor and postpartum. For infants, findings suggestive of pyloric stenosis will be assessed during the follow up visits. Maternal and neonatal surveillance will also include assessment of unintended medical visits, maternal deaths, stillbirths, neonatal death within 28 days of birth, and infant death after 28 days of birth. Additional maternal and neonatal risks associated with azithromycin use include anaphylaxis, allergic reactions (rash), liver failure, and arrhythmias. Although rare, these side effects will be monitored and reported as a serious adverse event. All safety outcomes will be reviewed at least twice a year by the Data Monitoring Committee (DMC) appointed by NICHD.

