3.5 Study Monitoring Plan

3.5.1 Reporting Serious Adverse Events

Serious Adverse events (SAEs) will be monitored continuously for any event that meets the following criteria:

- Results in neonatal/fetal or maternal death;
- Is life-threatening;

- Requires hospitalization or prolongs existing hospitalization;
- Results in persistent or significant disability or incapacity;
- Suspicion of pyloric stenosis within 42 days postpartum (prolonged vomiting leading to death or surgery)
- Any other serious or unexpected adverse event that the study investigator(s) feels should be reported.

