Supplemental Infection Contact Form	To document signs of maternal or neonatal infection and provide referrals if indicated.	
 Maternal and neonatal infection danger signs. Referral information. 	Participant interview/report by phone
Maternal and Neonatal Unscheduled Medical Visit	To collect information about clinical events reported during follow-up visits	Reason for medical visit, details about medical visit	Participant interview/report, provider report, clinical exam, medical records
Specimen Collection and Result Form	To track specimen collection when there is indication of maternal or infant infection	Date/time of specimen collection; reason for collection; location of wound/infection; tracking information for shipping/storing specimen; results	Study documentation if collected and/or tested by study; medical records if collected and/or tested by health facility.
Serious Adverse Events	To record fatal, life-threatening, or any other serious, unexpected adverse event	Date/time of event, date/time of resolution, nature of adverse event, management of adverse event, attribution to study (yes/no).	Participant interview/report, provider report, medical records
Final Study Status	To document final study status	Final study status (e.g., completion, withdrawal, lost-to-follow-up), Date of final study status. If withdrawal, provide reason.	Participant report, medical records
Protocol Deviation	To record protocol deviations and corrective actions	Date and nature of deviation/violation, corrective action.	Participant report, study records, medical records
Outcome Adjudication	To validate cases of infection using standard study definitions	Primary and secondary outcomes	Study documentation, provider reports/interviews, medical records

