APPENDIX 3. SCHEDULE OF STUDY PROCEDURES

	ANC Visits	During Labor/ Before Delivery	After Delivery/ Before Discharge	3-day postpartum (pp)	7-day pp	14-day pp	28-day pp	42-day pp	As Needed
Community Sensitization	X								
Screening									
• Eligibility confirmation		X							
• Clinical assessment		X							
Consent		X							
Randomization		X							
Drug Administration		X							
Baseline Data Collection									
• Sociodemographic information		X	X						
• Medical history		X	X						
• Labor and delivery information			X						
Monitoring									
• Drug side effects		X	X	X	X			X	X
• Maternal events during labor/delivery		X	X						
• Neonatal events during labor/delivery			X						
• Maternal infection/sepsis assessment			X	X	X			X	X
• Neonatal infection/sepsis assessment			X	X	X			X	X
• Maternal death			X	X	X			X	X
• Stillbirth or neonatal death within 28 days of birth			X	X	X	X	X	X	X
• Infant mortality after 28 days of birth								X	X
• Pyloric stenosis			X	X	X			X	X
• Other maternal outcomes			X	X	X			X	X
• Other neonatal outcomes			X	X	X			X	X
• Unintended medical visits			X	X	X			X	X
Serious Adverse Events			X	X	X			X	X

STATISTICAL ANALYSIS PLAN

Prevention of maternal and neonatal death/infections with a single oral dose of azithromycin in women in labor (in low- and middle-income countries): a randomized controlled trial (A-PLUS)

The A-PLUS Study

SAP VERSION: Version 2.0

SAP DATE: October 13, 2022

SPONSOR: NICHD

PREPARED BY: RTI International
[name]
[name]

AUTHOR (S): [name], [name], [name]

Contents

1. BACKGROUND AND PROTOCOL HISTORY	6
2. PURPOSE OF THE ANALYSES	6
3. STUDY OBJECTIVES AND OUTCOMES	7
3.1 PRIMARY HYPOTHESIS AND ASSOCIATED OUTCOMES	7
3.2 SECONDARY AIMS AND ASSOCIATED OUTCOMES	8
4. STUDY METHODS	10
4.1 OVERALL STUDY DESIGN	10
4.2 STUDY POPULATION	11
4.3 STUDY ARM ASSIGNMENT AND RANDOMIZATION	12
4.4 MASKING AND DATA LOCK	12
5. ANALYSIS POPULATIONS	13
6. SAMPLE SIZE DETERMINATION	14
6.1 OVERALL (ALL-COMER) SAMPLE SIZE FOR PRIMARY OUTCOMES	14
6.2 HIGH RISK COHORT SAMPLE SIZE FOR PRIMARY OUTCOMES	16
7. STATISTICAL / ANALYTICAL ISSUES	17
7.1 GENERAL RULES	17
7.2 ADJUSTMENTS FOR COVARIATES	17
7.3 MISSING DATA APPROACHES:	17
7.4 MULTICENTER STUDIES	18
7.5 MULTIPLE COMPARISONS AND MULTIPLICITY	18
7.6 MASKED DATA REVIEW	18

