Neonatal admission to special care units	Binary	The outcome will be defined as “Yes” if there is an AZ04 or AZ08 form where the infant is noted as having received care or treatment at an intensive care or specialized care unit while at the facility; and “No” otherwise. The outcome will only be missing for infants that are lost to follow-up prior to completion of a Day 7 visit and had no specialized care reported prior to becoming LTF. Analysis population(s): ITT (all-comer and high risk)

Variable	Type	Definition
Neonatal Unscheduled Clinical or ER Visit	Binary	
The outcome will be defined as “Yes” if occurrence of unscheduled care after initial delivery discharge is reported on either AZ05b (with a non-missing date of care) or there is an AZ08 form (with a non-missing exact or estimated date of care); and “No” otherwise. The outcome will only be missing for infants that are lost to follow-up prior to completion of a Day 7 visit and had no unscheduled care visit reported prior to becoming LTF.
 
Analysis population(s): ITT (all-comer and high risk)

Pyloric stenosis within 42 days of delivery	Binary	
The event will be defined only for live births. The event will be defined as “Yes” if the infant is diagnosed with pyloric stenosis prior to day 42 and “No” otherwise.
 
The details of defining this outcome are in the adjudication plan. In brief, where possible the outcome will be defined programmatically per the algorithm defined in the adjudication plan with cases that are unable to be programmatically determined route to adjudication. For the adjudicated outcomes, the value will be determined based on the reported final outcome reported by the site via form AZ13 (and confirmed via central adjudication). If the final outcome is “Insufficient data to make a determination,” the outcome will be treated as missing.
 
Analysis population(s): As Treated

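### Pyloric stenosis has no scheduled check between days 7 and 42, and its SAP definition has no loss-to-follow-up rule, so infants lost after day 7 default to not having it

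*Combined protocol and SAP*

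**What the plan says.** **Outcome.** Protocol 2.7 sets a 42-day window, with the condition "defined as clinical suspicion based on severe vomiting leading to death, surgical intervention (pyloromyotomy) as verified from medical records, or radiological confirmation". SAP 3.2 repeats this. Protocol 1.6.3 says the trial's size allows the question to be explored further.

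**Schedule.** Protocol 2.8 states: "For infants, findings suggestive of pyloric stenosis will be assessed during the follow up visits". In Appendix 3 the row "Pyloric stenosis" is marked before discharge, on days 3, 7 and 42, and as needed. The day-14 and day-28 cells are empty.

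**Contacts on days 14 and 28.** Protocol 2.4.7: "Supplemental phone contacts will be conducted at 14-day and 28-day postpartum to review maternal and neonatal signs of infection using WHO criteria". The form for these contacts (Protocol 4.1) lists "Maternal and neonatal infection danger signs" and referral information. No vomiting, surgery or admission item is listed.

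**Other capture.** Protocol 2.4.7 provides a look-back: "Based on the scheduled visits, study staff will identify any unscheduled visits or readmissions", with readmissions then checked against records. Protocol 3.5.1 includes among the SAE criteria "Suspicion of pyloric stenosis within 42 days postpartum (prolonged vomiting leading to death or surgery".

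**Coding.** SAP 9.2 limits the outcome to live births. The event is Yes "if the infant is diagnosed with pyloric stenosis prior to day 42 and" No in every other case, except that adjudicated cases with insufficient data are missing. The row says nothing about loss to follow-up.

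**The concern.** A 42-day safety outcome is being collected and coded with tools built for infection. The day-14 and day-28 contacts do not ask about it, and the SAP's day-7 shortcut (an infant lost after a clean day-7 visit counts as event-free) is justified in 9.2 only by infections being expected mainly in the first week. The documents give no such reason for pyloric stenosis, and the choice of a 42-day window implies that later cases are of interest.

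An infant seen on day 7 and then lost enters the denominator as a negative although nobody asked about the remaining five weeks. A reassuring finding on a named infant harm would then rest partly on infants who were not observed.

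**Working it through.** The documents give no expected risk, sample size or power for pyloric stenosis, so there is no planned figure to reproduce.

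**1. Schedule.** From day 7 to day 42 is 42 − 7 = 35 days, or 35/42 = 83% of the window, without a scheduled check. The empty Appendix 3 cells do not prove this alone, because the infection rows are also blank on days 14 and 28 although 2.4.7 requires infection review then. The wording of 2.4.7 and the contents of the contact form settle it.

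**2. Coding, compared with other SAP 9.2 definitions.**

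| Definition | Lost before day-7 visit | Lost after day 7 |
|---|---|---|
| Preamble (infection, primary outcome) | missing if no signs of infection | no event if no signs of infection |
| Neonatal readmission, special care, unscheduled visit | missing if none reported before loss | No if none reported |
| All-cause neonatal death | missing if day-28 and day-42 outcomes are both missing | same rule |
| Pyloric stenosis | not stated | not stated; falls to No |

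The preamble may or may not govern the last row. It speaks of the primary outcome, and other rows restate its rule, which suggests that it is not automatic. SAP 5 says As Treated data are analysed as available whatever the later participation, which does not decide between No and missing.

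**3. Infants affected.** Loss rates: 1.1% in the pilot including withdrawals (SAP 7.3), and 2% to 3% planned (Protocol 3.2.1).

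- 34,000 × 0.011 = 374
- 34,000 × 0.02 = 680
- 34,000 × 0.03 = 1,020

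These are upper figures for losses after day 7, since the documents do not split loss by time.

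**4. Effect on absolute risk.** If a fraction d is lost, coded No and never ascertained, and loss is unrelated to the outcome, then observed risk = true risk × (1 − d). Setting these infants to missing raises the estimate by a factor of 1/(1 − d): 1.1% relative at d = 0.011, 2.0% at 0.02 and 3.1% at 0.03.

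In cases: with multiples at the midpoint of 1–2% and 1.8% intrapartum stillbirth, live births per arm are about 17,000 × 1.015 × 0.982 = 16,944. The true risk is an assumption, taken as 0.5 to 3 per 1,000, which gives 8.5 to 50.8 cases per arm. The number uncounted is 8.5 × 0.011 = 0.1 to 50.8 × 0.011 = 0.6 per arm at pilot loss, and 8.5 × 0.03 = 0.3 to 50.8 × 0.03 = 1.5 at 3% loss.

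**5. Effect on the relative risk.** The multiplier is (1 − d_azithromycin)/(1 − d_placebo).

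- Equal loss: 1.000
- Azithromycin 3%, placebo 2%: 0.97/0.98 = 0.990
- Azithromycin 3%, placebo 1%: 0.97/0.99 = 0.980

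**6. Detection among retained infants (illustration only).** The documents give no detection figure. Assume a true relative risk of 2, two-sided alpha 0.05 and 16,944 × 0.98 ≈ 16,605 infants per arm.

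| Assumed baseline per 1,000 | Power, full detection | Power, 75% detection | Power, 50% detection |
|---|---|---|---|
| 0.5 | 0.38 | 0.30 | 0.22 |
| 1 | 0.65 | 0.53 | 0.38 |
| 3 | 0.98 | 0.94 | 0.82 |

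Incomplete detection on this scale would cost more than the coding rule does, but nothing in the documents shows that it occurs.

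**The case against.** The strongest reply is that the outcome is a hard event (death, verified surgery or imaging) that leaves a record. For an infant who attends on day 42, the follow-up form covers status since discharge, including symptoms, clinic visits and hospitalizations. Neonatal death is checked on days 14 and 28. Participants are taught the signs of study outcomes and encouraged to call (Protocol 2.4.6). Poor feeding is among the protocol's pSBI signs, so an infection call could bring in an affected infant incidentally. A No default after day 7 also follows the convention in neighbouring rows, and derivation details are left to a separate adjudication plan that is not among these documents.

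This stands for retained infants. A reader might infer from the 83% figure that those days are unobserved, but the look-back, record review and SAE reporting cover them in part. It does not help infants who never reach day 42, and the convention carries over a reason that concerns infection.

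A reader might also infer that every undiagnosed infant, including those lost in week one, is coded No. The SAP does not establish that: stillbirths are outside the definition, insufficient-data cases are missing, and the 9.2 preamble may make losses before the day-7 visit missing.

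Nor should neonatal deaths be added to the count. At 2.3% they would be 34,000 × 0.023 = 782, but an infant who died of another cause without the condition did not have the event. Death is a competing event and No is correct; deaths from severe vomiting already fall under the 2.7 definition.

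On SAE wording, a case confirmed by imaging but not operated on meets 2.7 and not the bracketed SAE text. Hospitalization and the other SAE criteria would catch most such cases, so this is minor.

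**Conclusion.** The point holds as a gap in collection and an unstated coding rule. There is no scheduled check for pyloric stenosis between days 7 and 42 although two contacts take place in that interval, and live-born infants lost after day 7 default to No. The handling of earlier losses is ambiguous.

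The coding effect is small: at most 374 to 1,020 infants and about 1% to 3% relative understatement of absolute risk, with no change in relative risk if loss is equal by arm. This assumes that loss is unrelated to the outcome and that the adjudication plan holds no overriding loss rule. The effect would be larger if affected infants are more likely to be lost.

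The documents do not support the stronger conclusion that the risk is shown to be under-counted, because under-detection among retained infants is possible but not demonstrated. The case for acting is that the remedy is cheap and the harm is one the protocol itself names.

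**What to change.** 1. Add one item on persistent or severe vomiting, surgery or hospital admission in the infant to the Supplemental Infection Contact Form, and mark the day-14 and day-28 pyloric stenosis cells in Appendix 3.
2. In SAP 9.2, state the rule in the pyloric stenosis row. Undiagnosed live-born infants lost to follow-up before day 42 are missing, or censored at last contact. Deaths from other causes stay as non-events, with death as a competing event. Report the present No coding as a sensitivity analysis.
3. Reconcile the SAE wording in Protocol 3.5.1 with the outcome definition in 2.7.

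The cost is one question on contacts already made, one form revision and one SAP derivation change. The downsides are a few more referrals for benign vomiting, if positive answers follow the existing referral route, and a slightly smaller denominator. Item 2 needs no new data, so it remains possible even if follow-up is too far advanced for item 1.
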